**Note:**

Listing 16.2.5.1 will be used as the shell for the following listing:

Listing s16.2.5.1 – Treatment Administration at Visit 1/Day 1 for Subset of Rollover Subjects

Listing 16.2.5.2 – Touch-Up Treatment Administration at Visit 2/Week 2

Site-Subject	Analyses	No Touch-up Required for Either Side	Revanesse Ultra				Revanesse Ultra+			
			No Touch-up Required	Injection placed successfully?	Time of Injection	Amount of Syringe Used (ml)	Injected By	No Touch-up Required	Injection placed successfully?	Time of Injection

Analyses: I = Intent-to-Treat (ITT) Analyses only, M = Modified Intent-to-Treat (MITT) and ITT Analyses, P = Per-Protocol, MITT, and ITT Analyses.  
 O:\Studies\ Prollenium\SYM 2016-02\Biometrics\Programs\Listing\xxx.sas ran on Month Day Year at hh:mm on data from Month Day, Year.

**Note:**

Listing 16.2.5.2 will be used as the shell for the following listing:

Listing s16.2.5.2 – Touch-Up Treatment Administration at Visit 2/Week 2 for Subset of Rollover Subjects

Listing 16.2.6.1.1 – Efficacy Evaluations of Visual Analog Scale (VAS) for Pain

Site-Subject	Analyses	Study Visit	Time Point	Revanesse Ultra		Revanesse Ultra+	
				Time Assessed	Score	Time Assessed	Score
xx-xxxx	M	Visit 1/Day 1	Immediately After Injection	hh:mm	40	hh:mm	50

Analyses: I = Intent-to-Treat (ITT) Analyses only, M = Modified Intent-to-Treat (MITT) and ITT Analyses, P = Per-Protocol, MITT, and ITT Analyses.  
O:\Studies\ Prolenium\SYM 2016-02\Biometrics\Programs\Listing\xxx.sas ran on Month Day Year at hh:mm on data from Month Day, Year.

**Note:**

Listing 16.2.6.1.1 will be used as the shell for the following listing:

Listing s16.2.6.1.1 – Efficacy Evaluations of Visual Analog Scale (VAS) for Pain for Subset of Rollover Subjects

Listing 16.2.6.1.2 – Efficacy Evaluations (WSRS, pGAI, iGAI)

Site-Subject	Analyses	Study Visit	Treatment Arm	Wrinkle Severity Rating Scale (WSRS)		Patient Global Aesthetic Improvement (pGAI)	Investigator Global Aesthetic Improvement (iGAI)	
				Score	Performed By		Score	Performed By
xx-xxxx	M	...						
		Visit 2/Week 2	Revanesse Ultra	5=Extreme	XXX	2=No Change	1=Worse	XXX
			Revanesse Ultra+	3=Moderate	XXX	2=No Change	3=Improved	XXX

Analyses: I = Intent-to-Treat (ITT) Analyses only, M = Modified Intent-to-Treat (MITT) and ITT Analyses, P = Per-Protocol, MITT, and ITT Analyses.  
O:\Studies\ Prollenium\SYM 2016-02\Biometrics\Programs\Listing\xxx.sas ran on Month Day Year at hh:mm on data from Month Day, Year.

**Note:**

Listing 16.2.6.1.2 will be used as the shell for the following listing:

Listing s16.2.6.1.2 – Efficacy Evaluations (WSRS, pGAI, iGAI) for Subset of Rollover Subjects

*(Programmer note for Listing s16.2.6.1.2: Add Fitzpatrick Skin Type to the listing and present the data sorted by skin type.)*

Listing 16.2.6.2.1 – Primary and Secondary Efficacy Responses for Modified Intent-to-Treat Population

Site-Subject	Study Visit	Time Point	Revanesse Ultra		Revanesse Ultra+		Ultra minus Ultra+ in VAS	Responder*				
			Observed or MI	VAS Score	Observed or MI	VAS Score		Observed	MI	WSC	BCS	
xx-xxxx	III	Visit 1/Day 1	Immediately after injection	Observed	50	Observed	42	8	No			
			15 minutes post injection	Observed	46	MI	34.4	11.6	Yes	No	Yes	
			30 minutes post injection	Observed	31	MI	25.5	5.5	No	No	Yes	

Missing VAS scores for the mITT analysis will be replaced using the multiple imputation (MI) method. The average values from the MI copies of VAS are present and used for analysis. \*Responder (to Revanese Ultra+) is defined as a subject who had a within-subject difference (Revanese Ultra minus Revanese Ultra+) in VAS pain score of at least 10 mm on a 100-mm scale. Observed: Subjects are defined as responder or non-responder based on the non-missing values; MI (Multiple Imputation): Subjects with missing VAS scores are defined as responder or non-responder based on their VAS values through MI; WCS (Worst Case Scenario): Subjects with missing VAS scores are considered non-responders; BCS (Best Case Scenario): Subjects with missing VAS scores are considered responders.  
O:\Studies\ Prolenium\SYM 2016-02\Biometrics\Programs\Listing\xxx.sas ran on Month Day Year at hh:mm on data from Month Day, Year.

**Note:**

Listing 16.2.6.2.1 will be used as the shell for the following listing:

Listing s16.2.6.2.1 – Primary and Secondary Efficacy Responses for Modified Intent-to-Treat Population – Subset of Rollover Subjects

Listing 16.2.6.2.2 – Other Efficacy Responses for Modified Intent-to-Treat Population

Site-Subject	Study Visit	Wrinkle Severity Rating Scale (WSRS)		Patient Global Aesthetic Improvement (pGAI)		Investigator Global Aesthetic Improvement (iGAI)	
		Revanesse Ultra	Revanesse Ultra+	Revanesse Ultra	Revanesse Ultra+	Revanesse Ultra	Revanesse Ultra+
... XX-XXXX	... Visit 5/Week 12	5=Extreme	3=Moderate	3=Improved	4 =Much improved	4=Much improved	3=Improved

O:\Studies\ Prollenium\SYM 2016-02\Biometrics\Programs\Listing\xxx.sas ran on Month Day Year at hh:mm on data from Month Day, Year.

**Note:**

Listing 16.2.6.2.2 will be used as the shell for the following listing:

Listing s16.2.6.2.2 – Other Efficacy Responses for Modified Intent-to-Treat Population – Subset of Rollover Subjects

Listing 16.2.6.3.1 – Primary and Secondary Efficacy Responses for Per-Protocol Population

Site-Subject	Study Visit	Time Point	VAS Score			Responder*
			Revanesse Ultra	Revanesse Ultra+	Ultra minus Ultra+ in VAS	
xx-xxxx	Visit 1/Day 1	Immediately after injection	50	42	8	No
		15 minutes post injection	46	34	12	Yes
		30 minutes post injection	31	25	6	No

\*Responder (to Revanese Ultra+) is defined as a subject who had a within-subject difference (Revanese Ultra minus Revanese Ultra+) in VAS pain score of at least 10 mm on a 100-mm scale.

O:\Studies\ Prollenium\SYM 2016-02\Biometrics\Programs\Listing\xxx.sas ran on Month Day Year at hh:mm on data from Month Day, Year.

**Note:**

Listing 16.2.6.3.1 will be used as the shell for the following listing:

Listing s16.2.6.3.1 – Primary and Secondary Efficacy Responses for Per-Protocol Population – Subset of Rollover Subjects

Listing 16.2.6.3.2 – Other Efficacy Responses for Per-Protocol Population

Site-Subject	Study Visit	Wrinkle Severity Rating Scale (WSRS)		Patient Global Aesthetic Improvement (pGAI)		Investigator Global Aesthetic Improvement (iGAI)	
		Revanesse Ultra	Revanesse Ultra+	Revanesse Ultra	Revanesse Ultra+	Revanesse Ultra	Revanesse Ultra+
...	...						
XX-XXXX	Visit 5/Week 12	5=Extreme	3=Moderate	3=Improved	4 =Much improved	4=Much improved	3=Improved

O:\Studies\ Prollenium\SYM 2016-02\Biometrics\Programs\Listing\xxx.sas ran on Month Day Year at hh:mm on data from Month Day, Year.

**Note:**

Listing 16.2.6.3.2 will be used as the shell for the following listing:

Listing s16.2.6.3.2 – Other Efficacy Responses for Per-Protocol Population – Subset of Rollover Subjects

Listing 16.2.7.1 – Adverse Events

Site- Subject	Analy	Skin Type	AE Reported by	System Organ Class// Preferred Term// Verbatim Term	Start Date [Day #]	Stop Date [Day #]	Severity	Causality	Action Taken 	Out 	Serious?
Treatment: Revanesse Ultra											
...											
...											
...											
Treatment: Revanesse Ultra+											
...											
...											
...											
Treatment: Unidentified (not on face)											
...											
...											

Analyses (Analyses): I = Intent-to-Treat (ITT) Analyses only, M = Modified Intent-to-Treat (MITT) and ITT Analyses, P = Per-Protocol, MITT, and ITT Analyses.

Day # is calculated from baseline (Visit 1) date. Day 1 is the baseline date while Day -1 is the day prior to the baseline visit.

 Action Taken: 1=None, 2=Study treatment interrupted/discontinued, 3=Non-drug therapy, 4=New OTC or Rx drug added, 4=Hospitalized

 Out (outcome): 1= Resolved, 2=Improved, 3=Stabilized, 4=Worsened, 5=Unchanged, 6=Lost to Follow-up/Unknown, 7=Fatal

O:\Studies\ Prolenium\SYM 2016-02\Biometrics\Programs\Listing\xxx.sas ran on Month Day Year at hh:mm on data from Month Day, Year.

**Programming Note:** Each AE is identified with the associated treatment arm or as a systemic event based on how the field is filled on the CRF for “If AE located on face”.

- If it is left blank, the event is considered systemic and is to be reported under the grouping for “Treatment: Unidentified (not on face)”.
- If it is filled as on the Left Side or the Right Side, the event is to be identified with the proper treatment arm and is to be reported under the proper treatment arm.
- If it is filled as on Both Sides, the event is to be reported once under each treatment arm.

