8.6.14 Subject Diary Card

A diary card will be dispensed to each enrolled subject at Visit 1/Day 1. The subject will be instructed to complete the diary card to record any AEs experienced during the 2 weeks after receiving treatment. The diary card will be collected at Visit 3/Week 4. A diary card will be dispensed at Visit 2/ Week 2 if a touch-up treatment is administered. The diary card will be collected at Visit 4/Week 12.

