8.9 Assessment of Safety

8.9.1 Safety Endpoints

Safety of the study products will be compared by evaluating the nature, severity, and frequency of treatment-emergent adverse events (TEAEs). All AEs that occur during the study will be recorded whether or not they are considered to be related to treatment. A description of the AE will be recorded with the date of onset, date of resolution, severity of the AE, relationship to the study product, action taken, and the outcome.

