### 5.6.1 Adverse Events

All adverse events (AEs) occurring during the study will be recorded and coded in the Medical Dictionary for Regulatory Activities (MedDRA), version 15.1 or higher. TEAEs are defined as events that appear subsequent to the first injection or that were present prior to the first injection but worsened in intensity after the first injection. TEAEs may include, but are not limited to, injection site bruising, injection site discoloration, injection site edema, injection site erythema, injection site inflammation, injection site pain, and injection site swelling.

Frequency and percent of subjects reporting TEAEs of injection site reactions will be tabulated for each treatment by system organ class and preferred terms, and further by severity. In summaries of severity, subjects who reported more than one event in a treatment arm that are mapped to the same preferred term will be counted only once in that treatment arm under the strongest severity.

For other AEs where an association with either treatment may not be clearly identified, including systemic TEAEs, frequency and percent of subjects will be tabulated to treated subjects as one group by system organ class and preferred terms, and further by severity and relationship to study device. In summaries of severity and relationship, subjects who reported more than one event that are mapped to the same preferred term will be counted only once under the strongest severity and relationship.

Injection-site TEAEs and non-injection site TEAEs will also be tabulated by subject Fitzpatrick Skin Type (I-IV vs. V-VI) and by number of injections subjects received. Summary by preferred term will further be provided for TEAEs that are reported by subject and for TEAEs that are reported by Investigator separately. Most frequently occurring injection site TEAEs will also be summarized by event's severity and duration.

Treatment-Emergent Serious Adverse Events (TESAEs) will be discussed within the clinical study report. TESAEs and TEAEs that led to treatment interruption or discontinuation will be presented in data listings.

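### An adverse event marked 'Both Sides' carries one severity and one pair of dates to both products, so those records cannot show a product difference in the severity and duration tables

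*SAP*

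**What the plan says.** Protocol section 8.9.1 sets the comparison: "Safety of the study products will be compared by evaluating the nature, severity, and frequency of treatment-emergent adverse events (TEAEs"). The same section describes what is recorded for each event: "A description of the AE will be recorded with the date of onset, date of resolution, severity of the AE", followed by relationship, action and outcome. It does not mention sides. The diary (protocol 8.6.14) asks subjects to "record any AEs experienced during the 2 weeks after receiving treatment", again without asking for left and right separately.

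The programming note under SAP Listing 16.2.7.1 links each event to a product or treats it as systemic "based on how the field is filled on the CRF for" location on the face. It has three branches:

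- One side: "If it is filled as on the Left Side or the Right Side, the event is to be identified with the proper treatment arm".
- Both sides: "If it is filled as on Both Sides, the event is to be reported once under each treatment arm".
- Blank: "If it is left blank, the event is considered systemic and is to be reported under the grouping for" events of unidentified treatment, labelled as not on the face.

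The listing shell has one column each for start date, stop date, severity, causality, action and outcome. For the severity tables, SAP 5.6.1 says that a subject with several events of one preferred term in an arm "will be counted only once in that treatment arm under the strongest severity". Table 14.3.2.8 applies the matching rule with the longest duration.

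**The concern.** The split-face design lets each subject serve as their own control. Pain, WSRS, pGAI and iGAI are all scored for each fold (protocol 8.6.7, 8.6.8, 8.6.12, 8.6.13), and the dispensing log records product used per fold (11.2.1). A 'Both Sides' adverse event loses that contrast. Suppose swelling is moderate for 10 days on one fold and mild for 3 days on the other, and the site enters it as one 'Both Sides' line. The tables then count it as the same severity and the same duration for both products.

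The affected outputs are the by-product severity and duration tables: 14.3.2.2, 14.3.2.6, 14.3.2.7 and 14.3.2.8. Table 14.3.2.6 also splits by causality, outcome and action taken. SAP Amendment 2 added the last three tables in answer to an FDA labeling request made for study SYM 2014-02, so they may well be read as product comparisons. Incidence is not the problem: a reaction present on both folds should count once for each product. What is lost is any difference in how bad it was and how long it lasted.

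The blank branch raises a related issue. An injection-site term with no location ticked leaves both product columns and is listed as systemic.

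**Working it through.** The documents state no figure on this point, so the check is of the data structure, followed by an illustration.

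**Step 1: what one record can carry.** The listing row has one value per attribute. The note sends a 'Both Sides' row to both arms and gives no rule for side-specific values. For that row, Ultra minus Ultra+ is therefore exactly 0 for severity, duration, causality, action and outcome.

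**Step 2: where a difference can still appear.** A bilateral reaction entered as one Left and one Right record keeps its own values under the one-side branch. A subject with a 'Both Sides' record plus a worse or longer one-sided record of the same term can also differ between arms, through the strongest-severity and longest-duration rules.

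**Step 3: size.** Write the true difference as D = D1 + D2, where D1 comes from one-sided reactions and D2 from bilateral ones. Let f be the share of truly different bilateral reactions entered as 'Both Sides', taken as equal in both directions. Then

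shown difference = D1 + (1 − f) × D2.

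Illustration, with all rates assumed: 100 subjects, each with one bilateral reaction (so D1 = 0). It is moderate or worse on the Ultra fold only in 20%, on the Ultra+ fold only in 5%, on both in 10% and on neither in 65%. The true rates are 20 + 10 = 30% and 5 + 10 = 15%, so D2 = 15 points. If a copied record carries the worse fold's severity, the shown rates are 30 + 5f for Ultra and 15 + 20f for Ultra+:

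| f | Ultra | Ultra+ | Shown difference |
|---|---|---|---|
| 0 | 30.0% | 15.0% | 15.0 points |
| 0.25 | 31.25% | 20.0% | 11.25 points |
| 0.50 | 32.5% | 25.0% | 7.5 points |
| 0.75 | 33.75% | 30.0% | 3.75 points |
| 0.90 | 34.5% | 33.0% | 1.5 points |
| 1 | 35.0% | 35.0% | 0 points |

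The shown difference does not depend on which fold's severity is entered, since both arms receive it. The documents do not give f.

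**Step 4: what repeating the tables without copied records shows.** Take f = 0.5, with the entry style unrelated to the reaction. Fifty subjects remain, with 15 moderate-or-worse reactions on Ultra (30% of 50) and 7.5 on Ultra+ (15% of 50). Tables 14.3.2.7 and 14.3.2.8 use subjects with the reaction as denominator, so there the 15-point difference returns. Table 14.3.2.2 and the subject columns of 14.3.2.6 use all treated subjects, so the difference stays at 15% − 7.5% = 7.5 points and only the levels fall. The count of copied records is therefore needed alongside the repeat.

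**The case against.** The strongest reply is that the note already accommodates separate records. A site that sees different reactions on the two folds can enter Left and Right lines, and each goes only to its own product. The CRF page and its completion instructions are not in the documents and may already say when to split. If sites use 'Both Sides' mainly when the folds look alike, little is lost. The safety tables are descriptive, so no test, claim or sample size depends on them, and injection pain, the primary endpoint, is scored per fold by VAS. A blank location for an injection-site term is a completion error, and monitoring and data correction forms (protocol 11.2.1 and 11.3) exist for such errors.

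Much of this stands, and it rules out three stronger conclusions that a reader might draw:

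- That severity and duration can never differ between products for a bilateral reaction. Step 2 shows two ways in which they can.
- That the tables will show no effect of lidocaine whatever the truth. One-sided events still count for one product only.
- That any true difference shrinks in proportion to the share of all injection-site events marked 'Both Sides'. If the whole difference comes from one-sided reactions (D2 = 0), it is shown in full whatever that share is.

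The reply does not show that split entry is required. Nothing in the protocol or SAP requires it, and nothing tells a reader of the tables how many ties were created by copying. General data-correction procedures do not specify a query for these entries.

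**Conclusion.** The point holds for records marked 'Both Sides': they show no product difference in severity, duration, causality, action or outcome by construction, in tables meant to support a stated comparison of severity. The bias is toward no difference. Its size cannot be computed from the documents. It depends on how many truly different bilateral reactions are entered on one line, and could range from nothing (f = 0) to the loss of the whole bilateral contrast (f = 1).

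Two assumptions carry this: that the CRF record has the same single-value structure as the listing shell and protocol 8.9.1, and that no site instruction outside the protocol and SAP requires split entry. The 15-point example adds assumed rates and an f that is equal in both directions. The primary analysis is untouched. This should be corrected because the safety comparison is an objective and the remedy is cheap.

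**What to change.** 1. In the CRF completion instructions, require injection-site reactions to be entered as one line per fold, Left or Right, each with its own severity, dates and outcome.
2. Before database lock, query every 'Both Sides' and every blank location for an injection-site preferred term.
3. For records that stay 'Both Sides', footnote their number in Tables 14.3.2.2 and 14.3.2.6 to 14.3.2.8, and repeat those tables without them. Treat the repeat as a sensitivity analysis, because dropping these records also removes reactions that really were symmetrical.
4. List unresolved blank injection-site terms in a separate row for side not recorded. Do not class them as systemic, and do not copy them to both products, which would repeat the fault and could charge a one-sided event to the wrong product.

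The cost is more adverse event lines, a round of queries, a short change to the programming note and one extra set of tables. Timing limits item 1. SAP Version 3.0 is dated 21 July 2017, and Amendment 2 of the same date refers to the interim analysis as done; that analysis was planned for after all subjects had completed Visit 3 or discontinued. For events already collected, only the queries, the footnote, the separate row and the sensitivity tables may be feasible, and side-specific detail should be changed only where source documents support it.

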**Note:**

Repeat [Listing 16.2.7.1](#) for AEs that led to study treatment interrupted/Discontinued and Serious AEs –

Listing s16.2.7.1 – Adverse Events for Subsets of Rollover Subjects

Listing 16.2.7.2 – Adverse Events Leading to Study Treatment Interrupted/Discontinued

Listing s16.2.7.2 – Adverse Events Leading to Study Treatment Interrupted/Discontinued for Subsets of Rollover Subjects

Listing 16.2.7.3 – Serious Adverse Events

Listing s16.2.7.3 – Serious Adverse Events for Subset of Rollover Subjects

Listing 16.2.7.4 – Injection Site Adverse Events Lasted more than 30 Days

Listing 16.2.8.1 – Vital Signs and Urine Pregnancy Test at Baseline

---

Site-Subject	Analyses	Sitting Systolic BP (mmHg)	Sitting Diastolic BP (mmHg)	Heart Rate (bpm)	Oral Temperature (°F)	Respiratory Rate (breath/min)	Urine Pregnancy Test	
							Test Results	Test Date

---

Analyses: I = Intent-to-Treat (ITT) Analyses only, M = Modified Intent-to-Treat (MITT) and ITT Analyses, P = Per-Protocol, MITT, and ITT Analyses  
O:\Studies\ Prolenium\SYM 2016-02\Biometrics\Programs\Listing\xxx.sas ran on Month Day Year at hh:mm on data from Month Day, Year.

Listing 16.2.9.1 – Prior and Concomitant Medications/Treatments

Site-Subject	Analy	Treatment Assignment	If Used on Face	WHO Class // WHO Name // Medication	Indication	Start Date [Day #]	Stop Date [Day #]	Dosage	Freq.	Route
xx-xxxx	P	L:Ultra, R:Ultra+	L, R	XXXXXXXXXX // XXXXXXXXXXXXX XXX // XXXXXXXXXXXXX	XXXXXXXX	01JAN05 [3]	Ongoing	xxxxx	xxxx	xxx

Analy (Analyses): I = Intent-to-Treat (ITT) Analyses only, M = Modified Intent-to-Treat (MITT) and ITT Analyses, P = Per-Protocol, MITT, and ITT Analyses.

Note: Medications coded using the WHO Drug Dictionary, version xxx.

Day # is calculated from baseline (Visit 1) date. Day 1 is the baseline date while Day -1 is the day prior to the baseline visit. L=Left side of the face, R=Right side of the face.

O:\Studies\ Prollenium\SYM 2016-02\Biometrics\Programs\Listing\xxx.sas ran on Month Day Year at hh:mm on data from Month Day, Year.

Listing 16.2.9.2 – Non-Pharmacological Interventions (NPIs)

Site-Subject	Analy	Treatment Assignment	If Used on Face	Non-Pharmacological Intervention	Indication	Start Date [Day #]	Stop Date [Day #]	Dosage	Freq.	Route
xx-xxxx	P	L:Ultra, R:Ultra+	L, R	XXXXXXXXXXXXXXXXXXXX	XXXXXXXX	01JAN05 [3]	Ongoing	xxxxx	xxxx	xxx

---

Analy (Analyses): I = Intent-to-Treat (ITT) Analyses only, M = Modified Intent-to-Treat (MITT) and ITT Analyses, P = Per-Protocol, MITT, and ITT Analyses.  
 Day # is calculated from baseline (Visit 1) date. Day 1 is the baseline date while Day -1 is the day prior to the baseline visit. L=Left side of the face, R=Right side of the face.  
 O:\Studies\ Prolenium\SYM 2016-02\Biometrics\Programs\Listing\xxx.sas ran on Month Day Year at hh:mm on data from Month Day, Year.
